14.2 General description of statistical analyses

The statistical analysis of this trial will be performed as described and summarized in the protocol. Full details of the planned statistical analyses will be described in the trial statistical analysis plan.

The statistical analysis of this trial will be planned, performed, and reported by sponsor personnel or by authorized sponsor delegates, in accordance with sponsor SOPs/SOPs of the sponsor's delegate.

Data collected and derived in the trial will be listed.

Summary statistics and graphical methods will be used to describe endpoints of interest.

The following descriptive statistics will be produced on the basis of the nature of the relevant statistical variable:

- For continuous variables: number of non-missing observations, arithmetic mean, standard deviations, minimum, first quartile (Q1), median, third quartile (Q3) and maximum.
- For categorical variables: frequencies and percentages.
- For time to event variables: number of non-missing observations, minimum, first quartile (Q1), median, third quartile (Q3), and maximum.

All the statistical analyses will be performed in the relevant analysis population of interest (see Section 14.3). All the statistical analyses will be performed at least by treatment group.

14.3 Analysis populations (analysis sets)

Enrolled Set

The Enrolled Set will comprise all subjects who signed the informed consent form.

Safety Set

The Safety Set will comprise all subjects allocated and treated with IMPs.

Analyses on the Safety Set will be conducted according to actual treatment received.

Full Analysis Set

The FAS will comprise all subjects allocated and treated, and with at least 1 non-missing pain relief assessment during the first 4 hours post-baseline. Analyses on the FAS will be conducted according to allocated treatment.

Per Protocol Set

The PPS will be defined as a subset of the subjects in the FAS without any major protocol deviations affecting the primary endpoint. Only subjects with no rescue medication use in the first 120 minutes after first dose, who complete at least a follow-up of 4 hours and who comply with the protocol procedures will be included in the PPS. Further details of the definition of the PPS will be specified in the statistical analysis plan.

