7.1 Definition of primary endpoint

Pain relief will be assessed at 15, 30, 45, 60, and 90 minutes, and at 2, 3, 4, 5, 6, 7, 8, and 16 hours after first dose using a 5-point verbal rating scale (VRS) with categories 0 (none), 1 (a little), 2 (some), 3 (a lot), or 4 (complete) (see Section 12.2.1.2).

The primary endpoint of the trial will be 4-hour Total Pain Relief (TOTPAR4). TOTPAR4 is a time-weighted measure of AUC up to 4 hours and is a summary measure that integrates serial assessments of a subject's pain over the duration of 4 hours after first dose.

TOTPAR4 scores will be calculated as $\sum PR_{t=4} \times [\text{time (hours) elapsed since previous observation}]$ where $PR_{t=4}$ is the Pain Relief at time point $t = 4$ in comparison to the assessment before administration of IMPs (Max and Laska 1991). For the first pain relief assessment, time (hours) elapsed since previous observation is time since first dose of IMP. Pain relief assessments after start of rescue medication intake (Section 10.5) will be set to missing and will be imputed as described in the statistical section (see Section 14.5.5).

Minimum and maximum potential value for TOTPAR4 are 0 and 16 points, corresponding to a value of 0 (none) or 4 (complete) at all pain relief assessments in the first 4 hours after first dose, respectively.

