10.5 Rescue medication

Details on rescue medication are provided in Section 1.4.2.

Subjects can request and take rescue medication at any time after the first administration of the IMPs if their trial medication does not provide sufficient pain relief. However, they will be encouraged (but not required) to refrain from rescue medication intake until at least 120 minutes after the intake of the first dose of IMPs (i.e., until diclofenac and tramadol have reached their maximum plasma concentration) to be able to reliably assess the efficacy of the IMPs first.

The time will be registered when subjects first request rescue medication and the time they take their first dose. Subjects taking rescue medication will be asked to complete the trial procedures as planned.

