14 QUANTITATIVE ANALYSES

14.1 Statistical methods and sample size determination

14.1.1 Sample size rationale

A total number of 720 subjects or 180 subjects per treatment group are required to achieve an overall power of at least 85% to reject the null hypothesis of at least 1 of the 4 formal statistical tests in the primary analysis of the trial (1-sided t-test, type I error of $\alpha/4$ with $\alpha = 2.5\%$) assuming a common standard deviation of change from baseline values of 4 points (TOTPAR4) (Bakshi et al. 1994, Hersh et al. 2004) and an expected treatment difference of at least 2 points (TOTPAR4) (Aquad et al. 2009, Singla et al. 2014) on the primary efficacy endpoint in the comparisons between tramadol HCl/diclofenac sodium 50 mg/50 mg and the monotherapies of diclofenac sodium 50 mg and tramadol HCl 50 mg, and using a non-inferiority margin of $\Delta = 1.5$ points (TOTPAR4) (see Section 18.2) on the primary efficacy endpoint in the comparisons between tramadol HCl/diclofenac sodium 25 mg/25 mg and the monotherapies of diclofenac sodium 50 mg and tramadol HCl 50 mg. To achieve 180 evaluable subjects per arm and accounting that up to 10% of subjects will not be evaluable for the analysis set for the primary analysis, 200 subjects per arm or 800 subjects in total will be allocated to IMP.

Assuming an enrollment failure rate of about 25% which is usually observed in clinical trials in Mexico, about 1065 subjects are planned to be enrolled (i.e., sign the informed consent) in order to allocate 800 subjects to IMP, i.e., about 130 subjects per trial site in approximately 8 to 12 sites.

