14.5.5 Missing data

Diligent attempts will be made to limit the amount of missing data in the pain relief assessments used to determine the primary efficacy endpoint. Efforts will be made to encourage but not to enforce subjects to not start rescue medication intake if not needed.

Primary analysis

For the primary analysis, missing pain relief assessments in the first 4 hours after first dose as well as pain relief assessments after start of intake of rescue medication will be imputed by LOCF for intermittent missing data, and substitution by δ for missing data after premature discontinuation from the trial or disregarded pain relief assessments after start of rescue medication intake.

The value of parameter δ will depend on the reason for discontinuation and treatment arm. The following 3 categories of reason for discontinuation will be distinguished: Discontinuation due to LoE, adverse events, and other, non-drug related reasons. The parameter will be

- $\delta = 0$: For missing data after discontinuation due to LoE, discontinuation due to adverse events and for disregarded pain relief assessments after start of rescue medication intake for subjects in the tramadol HCl/diclofenac sodium FDC combination arms.
- $\delta = 0.375$: For missing data after discontinuation due to LoE, discontinuation due to adverse events and for disregarded pain relief assessments after start of rescue medication intake for subjects in the monotherapy arms diclofenac sodium 50 mg and tramadol HCl 50 mg.
- $\delta = 0$: For missing data after discontinuations due to other, non-drug related, reasons.

The size of parameter δ is chosen to result in a TOTPAR4 penalty of $\Delta/2$ in case the trial discontinuation/start of rescue medication intake occurs 2 hours after first dose, with non-inferiority margin $\Delta = 1.5$ points (TOTPAR4) as determined in Section 18.2.

Sensitivity analysis 1: Full Analysis Set, single imputation methods

To investigate the constancy assumption, missing and disregarded pain relief assessments will be imputed with the following single imputation methods used in historical trials of the active comparators as well:

- Last Observation Carried Forward.
- Last Observation Carried Forward for intermittent missing data, and substitution by Zero (no relief from starting pain) for missing data after premature discontinuation from the trial or disregarded pain relief assessments after start of rescue medication intake.

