8.3 Handling of Dropouts or Missing Data

Diligent attempts will be made to limit the amount of missing data in the pain relief assessments used to determine the primary efficacy endpoint. Efforts will be made to encourage but not to enforce subjects to not start rescue medication intake if not needed. Assessments with missing date/time of evaluation will be considered unreliable and removed from all analyses and treated as missing values. Assessments made after the subject's first dose of rescue medication will be considered missing values and excluded from the analyses. Other than the methods outlined below for TOTPAR4, TOTPAR6, and TOTPAR8, no imputations will be performed to replace missing values for any of the other endpoints; those missing values will be left as missing.

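### The Full Analysis Set requires a usable relief rating, so treated subjects lost before any rating (and, read literally, those rescued before one) leave the primary analysis although the plan's own substitution rule could score them

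*Protocol*

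**What the plan says.** Protocol 14.3 limits the FAS to allocated and treated subjects "with at least 1 non-missing pain relief assessment during the first 4 hours post-baseline". Protocol 1.6.2, the SAP definitions and SAP 6 say the same. Protocol 14.5.3.1 and SAP 9.1 make the FAS the primary set for every comparison.

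Four other provisions decide who can meet that condition:

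- Timing of ratings (Protocol 7.1): "Pain relief will be assessed at 15, 30, 45, 60, and 90 minutes", then from 2 hours onward. The first chance to qualify is at 15 minutes.
- Timing of rescue (Protocol 10.5): "Subjects can request and take rescue medication at any time after the first administration of the IMPs". Waiting 120 minutes is encouraged, not required.
- Status of ratings after rescue: "Pain relief assessments after start of rescue medication intake (Section 10.5) will be set to missing" (Protocol 7.1). SAP 8.3 says that assessments after the first dose of "rescue medication will be considered missing values and excluded from the analyses". It treats ratings without a date or time in the same way.
- Collection after rescue (Protocol 10.5): "Subjects taking rescue medication will be asked to complete the trial procedures as planned".

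Protocol 14.5.5 and SAP 8.3.1 then provide a substitution. "The value of parameter δ will depend on the reason for discontinuation and treatment arm": 0 in the FDC arms, 0.375 in the monotherapy arms after rescue or after discontinuation for lack of efficacy or an adverse event, and 0 in any arm after discontinuation for other reasons.

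**The concern.** Membership of the primary set depends on something observed after randomisation, and for the earliest failures it can depend on the outcome itself. Protocol 14.5.1 chooses the FAS for the non-inferiority tests because it keeps the benefit of randomisation. It also asks for conservative handling, so that early leavers do not make the arms look more alike than they are. Dropping subjects who fail or leave before the first usable rating sits poorly with that reasoning, particularly as the plan already has a score for them.

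The sensitivity analyses do not fill the gap. Those in SAP 8.3.2 and 9.2.1 run on the FAS, and the one in SAP 9.2.2 runs on its subset, the Per Protocol Set. SAP 8.3.2 even lets the worst-observation rule reach back to baseline, which would score a subject rescued before any rating, but only if that subject is in the FAS.

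At stake is a possible shift in the FDC-minus-monotherapy contrast for the tests against the 1.5-point margin (T3, T4), and to a lesser degree for the superiority tests. There is also a risk that two programmers build different primary sets from the same text.

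**Working it through.** **Plan's own figures.** Each one reproduces.

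- Sample size (Protocol 14.1.1): SD 4, margin 1.5, one-sided alpha 0.025/4 = 0.00625, power 85%. The true difference for non-inferiority is not stated, so 0 is assumed. n = 2 × (4/1.5)² × (2.498 + 1.036)² = 178 per arm by the normal approximation; with the noncentral t, 180 per arm gives 85.2%. 180/0.90 = 200 per arm. The allowance is thus up to 20 per arm, or 80 of 800.
- TOTPAR4 weights: 4 × 0.25 + 2 × 0.5 + 2 × 1 = 4 hours, and 4 × 4 = 16, the stated maximum.
- Delta: 2 hours × 0.375 = 0.75 = 1.5/2, the stated penalty for an event at 2 hours.

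**Who is excluded.**

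1. A subject who leaves before any rating has none, so exclusion is certain.
2. A subject who takes rescue before any rating may still have ratings collected afterwards. If these are blanked first and FAS membership is judged second, the subject is out. If membership is judged on collected ratings, the subject is in and delta applies from time 0. Protocol 7.1, SAP 8.1.1 and SAP 8.3 favour the first order, but neither document states it.

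**Score if included.** With every rating substituted, TOTPAR4 is 4 × 0 = 0 in the FDC arms, and in any arm after discontinuation for other reasons. It is 4 × 0.375 = 1.5 in a monotherapy arm after rescue, lack of efficacy or an adverse event.

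**Shift in the contrast.** Let m be the mean among retained subjects, taken as equal in both arms, and let pF and pM be the shares lost early in the FDC and monotherapy arms. Including the lost subjects changes FDC minus monotherapy by

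−pF × m + pM × (m − 1.5).

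The documents give neither m nor the shares. I assume m = 6 to 8 and a share of 2%, which is 4 of 200 subjects.

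| FDC loss | Monotherapy loss | Shift, m = 6 | Shift, m = 8 |
|---|---|---|---|
| 2% | 0% | −0.12 | −0.16 |
| 2% | 2% | −0.03 | −0.03 |
| 0% | 2% | +0.09 | +0.13 |

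Against the margin, 0.12/1.5 = 8% and 0.16/1.5 = 11%. A negative shift means that the present FAS flatters the FDC; a positive shift means that it works against it.

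**The case against.** The case for leaving the definition alone has four parts.

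*The rescue exclusion is an inference.* This stands in part. Ratings continue after rescue, and Protocol 14.5.5 names disregarded post-rescue ratings separately from data missing after discontinuation. A reader might infer that everyone rescued before the first rating is certainly dropped; the text does not settle that. The ambiguity is itself a reason to clarify.

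*The window is short.* This stands. It is about 15 minutes, on site, with subjects encouraged to wait 120 minutes, and one rating before rescue is enough to qualify. Missed or untimed early ratings lengthen the window, but large numbers are unlikely.

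*The size could be exaggerated.* A reader might take the sample size allowance, that "up to 10% of subjects will not be evaluable for the analysis set for the primary analysis", and split it unevenly between arms to obtain a shift of several tenths of a point. The documents do not support this. The allowance is an overall ceiling, with no reasons and no split by arm. Multiplying a difference in rates by the mean would also ignore the 1.5 points that a substituted monotherapy subject can score.

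*The direction is open.* This stands. A reader might infer that the exclusion pulls the FDC toward non-inferiority. That requires more early loss in the FDC arm. Protocol 18.3 reports, from a bunionectomy trial, earlier onset and later rescue with the FDC than with diclofenac 50 mg, and the diclofenac comparator here is enteric-coated (Protocol 1.4.1). If monotherapy loses more, the exclusion can work against the FDC, which is conservative for T3 and T4.

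Nor is this a flat contradiction of Protocol 14.5.1, which does not promise that every treated subject will be analysed. Exclusions will also be visible in the disposition table (SAP 7.1) and Listing 16.2.3. Visibility does not put the subjects back into any analysis.

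**Conclusion.** The point holds in a limited form. Treated subjects with no rating are outside the primary set for certain, and those rescued before any rating are outside it on the literal but unstated order of steps. The existing substitution could score both groups, and no planned analysis restores them. The effect is probably small: 0.12 to 0.16 points for a 2% loss confined to the FDC arm, and about 0.03 for equal 2% loss with the monotherapy subjects scored 1.5. These figures rest on an assumed mean of 6 to 8, an assumed 2% rate and no difference among retained subjects. The sign is not known in advance. The case for change is that an avoidable post-randomisation exclusion and an ambiguity can be removed by wording alone, not that the trial's conclusion is in danger.

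**What to change.** Before unblinding, amend Protocol 1.6.2 and 14.3, the SAP definitions and SAP 6, with the matching scoring rule in Protocol 14.5.5 and SAP 8.3.1:

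1. Define the FAS as all allocated and treated subjects, analysed as allocated.
2. Where no usable rating precedes rescue or discontinuation, apply the existing delta substitution from time 0.
3. Where there is no usable rating for any other reason (for example, all ratings untimed), set relief to 0, the starting value, since there is nothing to carry forward.
4. Keep the present definition as a sensitivity set, and state whether non-missing is judged before or after post-rescue ratings are blanked.

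This needs no new data and no change in sample size. The cost is that a few subjects carry a fully substituted score. Under the delta rule that score is 1.5 in a monotherapy arm after rescue, lack of efficacy or an adverse event, against 0 in an FDC arm. For those subjects the gap equals the margin, and it should be acknowledged when results are reported.

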14.4 Analysis of demographic data and other baseline characteristics

Subject disposition as well as demographic and baseline data and other subject characteristics (e.g., medical history and prior and concomitant medications) will be descriptively summarized for the Safety Set, FAS, and PPS.

14.5 Analysis of efficacy data

The primary analysis to investigate the primary objective of the trial (see Section 1.2) is based on the primary efficacy endpoint (TOTPAR4) and will be performed on the FAS and repeated as sensitivity analysis on the PPS. Additional sensitivity analyses and the analysis of additional efficacy parameters will be performed on the FAS only.

14.5.1 Analysis population for primary efficacy analysis

The primary analysis to investigate the primary objective of the trial (see Section 1.2) is based on the primary efficacy endpoint (TOTPAR4) and will be performed on the FAS.

The rationale to choose the FAS as analysis set for the non-inferiority comparisons of the primary analysis (for superiority comparisons the FAS population is used as a standard) is the preservation of the value of randomization and estimation of real world effectiveness, properties desirable for non-inferiority trials as well (Wiens and Zhao 2007). It is important to carefully choose conservative imputation methods (see Section 14.5.5) in order to avoid that subjects who discontinue the trial before full treatment effects are shown, diminish the difference between treatments making them appear more similar than they are and therefore inflate the risk of falsely accepting therapeutic non-inferiority when it is not justified. The primary analysis will be repeated as sensitivity analysis on the PPS. Additional sensitivity analyses and the analysis of additional efficacy parameters will be performed on the FAS only.

14.5.2 Overall testing strategy

The primary objective of the trial (see Section 1.2) is investigated by 4 formal statistical tests (see Table 1). Testing multiple hypotheses, however, may increase the family-wise type I error rate, the probability to erroneously reject at least 1 true null hypothesis, beyond the pre-specified significance level. In order to control the family-wise type I error rate in the strong sense at the pre-specified 1-sided significance level of $\alpha = 2.5\%$, a Bonferroni-Holm procedure (Holm 1979) will be used. The elementary null hypotheses H_{01} , H_{02} , H_{03} , and H_{04} and according statistical tests T_1 , T_2 , T_3 , and T_4 of the primary objective of the trial are listed in Table 1.

Table 1: Statistical tests and null hypotheses (all 1-sided) of the primary objective of the trial

Test	Description	Null hypothesis	Alternative hypothesis
T_1	Superiority of tramadol HCl/diclofenac sodium 50 mg/50 mg vs. tramadol HCl 50 mg	$H_{01}: \mu_{T50} - \mu_{ADL50/50} \geq 0$	$H_{A1}: \mu_{T50} - \mu_{ADL50/50} < 0$
T_2	Superiority of tramadol HCl/diclofenac sodium 50 mg/50 mg vs. diclofenac sodium 50 mg	$H_{02}: \mu_{D50} - \mu_{ADL50/50} \geq 0$	$H_{A2}: \mu_{D50} - \mu_{ADL50/50} < 0$
T_3	Non-inferiority of tramadol HCl/diclofenac sodium 25 mg/25 mg vs. tramadol HCl 50 mg	$H_{03}: \mu_{T50} - \mu_{ADL25/25} \geq \Delta$	$H_{A3}: \mu_{T50} - \mu_{ADL25/25} < \Delta$
T_4	Non-inferiority of tramadol HCl/diclofenac sodium 25 mg/25 mg vs. diclofenac sodium 50 mg	$H_{04}: \mu_{D50} - \mu_{ADL25/25} \geq \Delta$	$H_{A4}: \mu_{D50} - \mu_{ADL25/25} < \Delta$

ADL = Adorlan (tramadol HCl/diclofenac sodium); D = diclofenac sodium; T = tramadol hydrochloride; HCl = hydrochloride.

$\Delta = 1.5$ is the non-inferiority margin.

The trial will be positive if at least 1 of the according 4 statistical tests rejects the according null hypothesis.

According the Bonferroni-Holm procedure, the p-values of the 4 tests T_1 , T_2 , T_3 , and T_4 will be sorted in ascending order $p_{(1)} < p_{(2)} < p_{(3)} < p_{(4)}$ and the following algorithm will be applied to the corresponding null hypotheses $H_{(01)}$, $H_{(02)}$, $H_{(03)}$, $H_{(04)}$:

- Step 1. If $p_{(1)} < \alpha/4 = 0.625\%$, reject $H_{(01)}$ and move to the next step. Otherwise retain all null hypotheses and stop.
- Step 2. If $p_{(2)} < \alpha/3 = 0.833\%$, reject $H_{(02)}$ and move to the next step. Otherwise retain $H_{(02)}$, $H_{(03)}$ and $H_{(04)}$ and stop.
- Step 3. If $p_{(3)} < \alpha/2 = 1.25\%$, reject $H_{(03)}$ and move to the next step. Otherwise retain $H_{(03)}$ and $H_{(04)}$ and stop.
- Step 4. If $p_{(4)} < \alpha = 2.5\%$, reject $H_{(04)}$ and move to formally testing null hypotheses related to secondary endpoints. Otherwise retain $H_{(04)}$.

14.5.3 Analysis of primary endpoint

14.5.3.1 Primary analysis

The primary endpoint will be TOTPAR4 (see Section 7.1). The TOTPAR4 will be calculated as a weighted sum of the observed pain relief scores during the first 4 hours after first dose with weights proportional to the time since the last pain relief assessment. TOTPAR scores can be interpreted as estimates of the area under the longitudinal pain relief curve.

The estimand of interest for the primary efficacy analysis is the difference in the primary efficacy endpoint in all subjects in the FAS attributable to the initially allocated trial medication (Mallinckrodt et al. 2012). The FAS analysis will be the primary analysis for all comparisons.

Null hypotheses $H_{01} - H_{04}$ and alternative hypotheses $H_{A1} - H_{A4}$ of the formal statistical tests of the primary efficacy analysis are provided in Table 1. The primary analysis will use an ANCOVA model with treatment, site, and baseline pain (measured on an 11-point NRS) as covariates.

A detailed description of missing data imputation methods is provided in Section 14.5.5.

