11.1.2 Treatment Period (Visit 2 and Visit 3)

11.1.2.1 Allocation Visit (Visit 2)

For restrictions concerning meals and fluid intake before and after surgery, please see Section 11.2.3.

Standardized local anesthesia

Extraoral antiseptics will be performed with e.g., 2.0% chlorhexidine. Intraoral antiseptics will be performed with e.g., a 0.12% chlorhexidine rinse. To numb the mouth, blocking of the inferior alveolar, lingual, and buccal nerves will be carried out by using 1-3 cartridges of lidocaine plus epinephrine per third molar not exceeding a maximum total amount of 300 mg of lidocaine per subject (8.3 cartridges). The anesthetics will be provided as cartridges of 1.8 mL with 36 mg of lidocaine hydrochloride plus 0.018 mg of epinephrine. No other kind of anesthetic is allowed. The exact amount of lidocaine administered and times of administration must be documented in the CRF and the source document(s). Maxillary anesthesia will be obtained using local infiltration, posterior superior nerve blocks, and palatal blocks.

When the anesthetic takes effect, the tissue will be opened and the upper and lower molars will be extracted.

Standardized surgery

The dental surgery will be the extraction of 3 or more third molars. Incision from the anterior border of the mandibular ramus continued as a marginal incision to the mesiobuccal part of the mandibular third molar will be made. Thereafter, the buccal mucoperiosteal flap is elevated; bone is removed and irrigated with sterile physiologic saline solution. If necessary, splitting of the tooth will be performed. The ipsilateral maxillary third molar will be surgically removed, if indicated. The wounds will be cleaned, irrigated with sterile saline, and closed with sutures, if indicated.

Basic data of the surgical procedure performed, i.e., the number and position of the molars concerned (i.e., 01, 16, 17, or 32), duration (start/end time) of surgery, the degree of impaction of each tooth, and the extent of tissue damage must be recorded in the CRF and the source document(s).

Any deviations from surgical protocol must be thoroughly documented in the CRF. Deviations that may significantly influence postoperative pain assessments or safety and tolerability of the IMP will disqualify the subject for treatment allocation.

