Subjects requiring fourth molar extraction are allowed in the trial. Subjects with molars linked to the mandibular canal and those requiring immediate dental procedures other than third and fourth molar extraction must not be included in the trial.

Postoperative baseline examination and treatment allocation

After surgery, subjects will assess their pain on an 11-point NRS. Subjects who report at least moderate baseline pain intensity (≥ 5 on the NRS) within 4 hours after surgery will be allocated to treatment. If 4 hours elapse without the development of moderate to severe dental pain following the completion of surgery, subjects must not be allocated and must be discontinued from the trial.

The first dose of the IMPs (1 capsule or tablet with active treatment plus 3 placebos) will be administered as soon as subjects report a pain intensity ≥ 5 on the NRS. The time of dosing will be recorded. The use of cold compresses or ice bags on the cheeks of subjects is allowed 4 hours after the administration of IMP; their use must be avoided in the 30-minute period before each pain assessment.

Subjects who undergo surgery and receive IMPs will stay in the dental clinic or other research facility for at least 8 hours after the initial dose and will receive the second dose of IMPs at 8 hours (± 10 minutes). If pain assessments will take place in other research facilities, subjects must be transported to the facility between 15 minutes after the end of surgery and the first IMP administration; the commuting time may be up to 30 minutes. During transfer, subjects must be accompanied by a member of the SMO staff. Both must have written directions in the case of emergency.

Thereafter, they can leave the site and take their third dose of IMPs at home 16 hours (± 1 hour) after the first dose of IMPs. They will be asked to document the intake time and to return for Visit 3 the next day at a time which allows a pain assessment 24 hours after the initial IMP dose was given.

At the site, subjects will be provided with 2 stopwatches and a pain assessment booklet. They will be asked to record their pain assessments during the following 8 hours as follows.

- The baseline pain intensity score (11-point NRS) before the first dose of IMPs (Section 12.2.1.1).
- Pain intensity scores at 15, 30, 45, 60, and 90 minutes (± 2 minutes), and at 2, 3, 4, 5, 6, 7, 8 hours (± 6 minutes) after the first dose of IMPs (Section 12.2.1.1).

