7.3 Demographic and Baseline Characteristics

Demographic variables to be summarized include the following: date of signing the informed consent, age at informed consent (in years), gender, ethnicity, race, smoking status, height (in cm), weight (in kg), and body mass index (BMI). The BMI will be calculated.

Baseline characteristics, which includes information from the dental surgical procedure, will be summarized for the following: number of molars extracted, impacted molars classification, impacted molar position, planned surgical procedure, duration of surgery (minutes), amount of Lidocaine used during of surgery (mg), time from end of surgery to first dose of study medications (hours), and baseline pain intensity (both on the numeric 11-point rating scale and as categorized as none/mild/moderate/severe).

Demographic and baseline characteristics will be summarized for all the analysis populations (FAS, PPS and Safety Set).

The frequencies and percentages of subjects in the following categories of smoking status will be summarized: current smokers (every day or on some days per week), recent former smokers (smoked within the last 12 months), long-term former smokers (smoked 1 to more than 15 years ago), and never smoked regularly. The number of cigarettes/cigars/pipes smoked per week will be displayed in the listing for current smokers.

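### The primary ANCOVA uses no surgical covariate, although number of molars extracted and duration of surgery are fixed before allocation; this may forgo some precision, of practical interest only for T3 and T4

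*Protocol*

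**What the plan says.** Protocol 14.5.3.1: "The primary analysis will use an ANCOVA model with treatment, site, and baseline pain (measured on an 11-point NRS) as covariates". SAP 8.2 and 9.1 repeat these terms, with baseline pain continuous and site as a factor. The sensitivity analyses (Protocol 14.5.3.2; SAP 8.3.2 and 9.2) vary the imputation method and the analysis set, but never add a surgical covariate.

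Baseline pain is limited to NRS 5 to 10. The first dose "will be administered as soon as subjects report a pain intensity ≥ 5 on the NRS" (Protocol 11.1.2.1), and subjects who stay below 5 are not allocated.

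Surgery comes before allocation. Protocol 11.1.2.1 requires number and position of molars and start and end time of surgery to be documented, and adds that "the degree of impaction of each tooth, and the extent of tissue damage must be recorded in the CRF". SAP 7.3 treats number of molars extracted, duration of surgery and lidocaine amount as baseline characteristics, together with "time from end of surgery to first dose of study medications (hours"), but only for summary tables.

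On sample size, Protocol 14.1.1 says "A total number of 720 subjects or 180 subjects per treatment group are required", "assuming a common standard deviation of change from baseline values of 4 points (TOTPAR4"). It takes no credit for variance reduction by covariates.

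**The concern.** A covariate that is fixed before allocation and predicts the outcome shrinks the residual variance, and with it the standard error of every treatment contrast, without adding subjects. Of the model's two covariates, one (baseline NRS) has about half its scale cut off by the entry rule. The extent of surgery is a plausible further predictor of pain relief in the first four hours. The protocol itself treats surgery as relevant: under 11.1.2.1, surgical deviations that may significantly affect the pain assessments bar a subject from allocation.

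Standardization leaves some variation. Three or more third molars may be removed, tooth splitting is done only when needed, and duration is not fixed. If these differences predict TOTPAR4, the current model leaves that variance in the error term. What is at stake is the width of the intervals for T3 and T4.

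**Working it through.** **Inputs.** From Protocol 14.1.1: 180 evaluable subjects per arm, SD 4, margin 1.5, superiority effect 2, one-sided α = 0.025. From 14.5.2: Holm steps at α/4 = 0.00625, α/3, α/2 = 0.0125 and α. Two inputs are not in the documents and are assumed: a true difference of 0 for T3 and T4, and R², the share of residual TOTPAR4 variance that the added covariates explain beyond site and baseline pain. R² is shown as a range.

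**Step 1: reproduce 180 per arm.** For one non-inferiority test at α/4 with 85% power, the normal approximation gives

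n = 2 × 4² × (2.498 + 1.036)² / 1.5² ≈ 177.6, so 178 per arm.

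The exact t calculation gives 180, with power 85.2% at that size. So 180 per arm is what a single non-inferiority test needs. Allowing 10% non-evaluable, 180 / 0.9 = 200 per arm, as stated.

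**Step 2: power under the current model (normal approximation).** SE = 4 × √(2/180) = 0.4216.

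- T3 or T4 at α/4: Φ(1.5/0.4216 − 2.498) = Φ(1.060) = 85.5%.
- T3 or T4 at α/2: Φ(3.558 − 2.241) = Φ(1.316) = 90.6%.
- T1 or T2 at α/4: 98.8%.
- At least one of the four tests, simulated with arm means of 0 except 2 for the 50/50 arm: 99.9%. The planned "overall power of at least 85% to reject the null hypothesis of at least 1 of the 4 formal statistical tests" is met with room to spare.

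**Step 3: add covariates.** SD becomes 4 × √(1 − R²). The equivalent gain in sample size is 1/(1 − R²) − 1.

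| Assumed R² | SE | Equivalent n gain | T3 or T4 at α/4 | T3 or T4 at α/2 | T1 or T2 at α/4 |
|---|---|---|---|---|---|
| 0 | 0.422 | 0% | 85.5% | 90.6% | 98.8% |
| 0.02 | 0.417 | 2% | 86.3% | 91.2% | 98.9% |
| 0.05 | 0.411 | 5% | 87.5% | 92.1% | 99.1% |
| 0.10 | 0.400 | 11% | 89.5% | 93.4% | 99.4% |

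The α/2 column is the relevant one when T1 and T2 have already been rejected, which is likely under the design assumptions. Simulating the whole Holm procedure, including its last step at α, gives 93.5% for T3 under the current model and 93.9%, 94.6% or 95.7% at the three R² values. The direction is the same and the gain smaller.

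**Step 4: cost in degrees of freedom.** With 720 subjects and 8 sites, the current model leaves 720 − 1 − 3 − 7 − 1 = 708. Two more terms leave 706.

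**The case against.** The plan contains no error here. Both stratification factors, site and baseline pain, are in the model, and the sample size does not rely on any covariate. This stands in full.

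The gain is also unproven. The documents give no correlation between a surgical variable and TOTPAR4, and the design narrows what is left to explain. Subjects need at least three third molars with two impacted mandibular ones, only Class I and II molars qualify, lidocaine is capped at 300 mg, the surgery is standardized, and the site term may absorb differences between surgeons. This stands too, and it is why the size can be given only as a range starting at zero.

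Three stronger readings are tempting, but the documents do not support them:

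- *Precision is being given away in all four tests.* The standard error would shrink for all four if R² exceeds zero, but no R² is given, and T1 and T2 have almost no power left to gain.
- *Baseline scores cluster near 5, so baseline NRS is a weak covariate.* No baseline distribution is given, and neither is the frequency of pain checks before dosing, so a first qualifying score could be well above 5. The plan expects enough severe subjects to stratify on severity and analyze them as a subgroup.
- *Time from end of surgery to first dose is an equally clean baseline covariate.* It ends at dosing, and Protocol 10.3 places allocation before the first dose. Blinding makes an effect of treatment on it unlikely, but it is not fixed before allocation.

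**Conclusion.** The point holds as an optional efficiency improvement. The primary model leaves out two variables that are fixed before allocation, already collected and already classed as baseline characteristics in the SAP. It may therefore forgo some precision for T3 and T4.

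For an assumed R² of 2% to 10%, the gain per non-inferiority test is 0.8 to 3.9 percentage points of power at α/4, or 0.6 to 2.8 points at α/2. These figures rest on the protocol's SD of 4, 180 evaluable subjects per arm and a true difference of 0. At R² = 0 there is no gain.

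A reader might infer that the trial is underpowered or its primary test flawed. Neither follows: the 180 per arm reproduces without covariate adjustment, and type I error control is untouched.

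**What to change.** Before database lock and unblinding, add two pre-specified covariates to the primary TOTPAR4 ANCOVA: number of third molars extracted (3 versus 4) and duration of surgery in minutes. Do this by SAP amendment to 8.2 and 9.1, with matching wording in Protocol 14.5.3.1, because the protocol also fixes the primary model. State that a missing covariate value is replaced by the overall median. Report the current model as a sensitivity analysis. Leave out time from end of surgery to first dose.

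SAP 9.2.3, 9.3 and 9.4 borrow the primary model by cross-reference, as does Protocol 14.5.4 for TOTPAR6 and TOTPAR8. The amendment should therefore say whether those analyses keep the current terms; this point concerns TOTPAR4 only.

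The timing matters because SAP section 5 labels any analysis after unblinding as post-hoc. The cost is two model terms, about 2 of 700 degrees of freedom, and an amendment to both documents. No new data are needed.
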